Study Title: Intervention for Cognitive Reserve Enhancement in delaying the onset of Alzheimer's Symptomatic Expression (INCREASE) Study

ClinicalTrials.gov NCT02849639

Developed: December 14, 2015

Statistical analyses

We will use Student's t-tests (or Wilcoxon rank sum tests for non-normally distributed variables) and chi-square or Fisher's exact tests to assess the comparability of randomized study groups. To examine the effect of the intervention on prescribing appropriateness we will perform analysis of covariance (ANCOVA), with the dependent variables being the difference between MAI scores at baseline and the follow-up measure. We will control for any variables that might be significantly different between groups at baseline that have not already been included in the study protocol in regards to stratification of subjects.

Data evaluating cognitive reserve will be analyzed by intervention groups. For Aim 2, the impact on cognitive reserve will be assessed across the full range of SUVR (i.e., SUVR will be included in the analysis as continuous variable). If imbalance exists between groups after randomization, covariates for analysis will include age, gender, education, NART scores, and the number of targeted inappropriate medications using 2015 Beers Criteria. We will investigate change from baseline in CRCS by group using ANCOVA.

For the perceived health status measure, because the SF-36 does not produce a single overall measure and because of our concern regarding multiple comparisons, multivariate analysis of covariance (MANCOVA) will be used to simultaneously estimate the effect of the intervention on the eight SF-36 health concepts. Similarly, we will also control for any variables that might be significantly different between groups at baseline.

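### Randomisation is stratified by amyloid-PET positivity, but the SAP does not put the stratum in the MAI model or the by-group CRCS model; a smaller point is that other covariates enter only after a chance imbalance.

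*SAP*

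**What the plan says.** **Randomisation.** The protocol (Study Design; Research Procedures, Randomization) names one stratification factor, amyloid-PET positivity. It expects about 30 of the 90 participants to meet the amyloid threshold.

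**MAI model.** The SAP specifies an ANCOVA with "the dependent variables being the difference between MAI scores at baseline and the follow-up measure". The covariate rule is "We will control for any variables that might be significantly different between groups at baseline", restricted to variables "that have not already been included in the study protocol in regards to stratification of subjects".

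**CRCS model.** The SAP says "We will investigate change from baseline in CRCS by group using ANCOVA" and lists no stratum term. In the same paragraph, in the sentence on Aim 2, it says "SUVR will be included in the analysis as continuous variable". Five candidate covariates (age, gender, education, NART score, number of targeted Beers medications) are conditional: "If imbalance exists between groups after randomization, covariates for analysis will include age, gender, education, NART scores", and so on. The protocol repeats this condition in Study Design and in Randomization.

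**SF-36 model.** The rule is again a significance trigger: "we will also control for any variables that might be significantly different between groups at baseline".

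**Threshold.** The SAP names "tests to assess the comparability of randomized study groups" (t or Wilcoxon, chi-square or Fisher), but neither document gives a significance level or any other definition of imbalance.

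**The concern.** Stratified randomisation balances amyloid status between arms, so the treatment estimate varies less from trial to trial. A model without the stratum does not credit that gain. It counts the difference between strata as residual noise and reports too large a standard error. The test is then conservative and some power is lost. MAI and CRCS are both primary outcome measures under Specific Aim 1, so the models for both should be unambiguous.

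The secondary issue is how the other covariates are chosen. In a randomised trial, baseline differences between arms arise by chance. A rule that adjusts for whatever happens to differ selects covariates by chance imbalance, not by their expected relation to the outcome. With no stated threshold, two analysts could fit different models to the same data.

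**Working it through.** The documents give no power, effect size, SD or correlation, so there is no planned figure to reproduce. What follows is illustration under stated assumptions.

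**Inputs.** From the protocol: N = 90 and an expected 30 amyloid-positive, so strata of 30 and 60. Assumed: 1:1 allocation balanced within strata, two-sided 5% test, and a treatment effect of 0.5 SD of the analysed change.

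**1. Amyloid shifts change itself (plain change score).** Let g be the stratum effect on change, in within-stratum SDs. With balance within strata the true standard error is sqrt(4/90) = 0.211 SD, so the noncentrality is 0.5/0.211 = 2.37. Without the stratum, the model's residual variance is inflated by 1 + g² × (1/3)(2/3) = 1 + 2g²/9. The critical value of 1.987 is in effect multiplied by the square root of that factor.

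| g | multiplier | effective critical value | power, omitted | power, included | type I error, omitted |
|---|---|---|---|---|---|
| 0 | 1.000 | 1.987 | 65.0% | 65.0% | 5.0% |
| 0.2 | 1.004 | 1.996 | 64.7% | 65.0% | 4.9% |
| 0.5 | 1.027 | 2.042 | 63.0% | 65.0% | 4.4% |
| 0.8 | 1.069 | 2.124 | 59.9% | 65.0% | about 3.6% |

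Simulation with 100,000 replicates agrees: 63.1% v 65.2% at g = 0.5, and 59.7% v 65.0% at g = 0.8. Including the stratum when g = 0 costs nothing visible.

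**2. Amyloid shifts the level only.** A constant shift cancels in a plain change score, so the cost is nil (65.0% v 65.0%). The SAP does not name the baseline score as a covariate. If it were one, part of the level difference would stay in the residual. With a 0.8 SD level gap, power omitted v included is 63.1% v 64.6% at baseline-to-follow-up correlation r = 0.5, and 63.9% v 64.6% at r = 0.7. These two pairs are for an effect of 0.5 *residual* SD given baseline, so they are not on the scale of step 1. At 0.5 SD of change with r = 0.5 the pair is about 75.2% v 76.6%. On either scale the cost is about 1 to 2 points.

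**3. How often the covariate trigger fires.** For five independent covariates the chance that at least one differs at level a is 1 − (1 − a)^5: 22.6% at 0.05, 41.0% at 0.10 and 67.2% at 0.20. These rates hold for independent covariates only. At pairwise correlation 0.5 they are about 18%, 33% and 57%.

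**4. Triggered (p<0.05, one at a time) v always included, stratum in both.**

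| Covariate effect (assumed) | number | triggered | always |
|---|---|---|---|
| On level, R² 0.20, plain change, r 0.5 | 3 | 64.5% | 63.6% |
| same | 5 | 64.4% | 62.5% |
| On level, R² 0.20, baseline in model, r 0.5 (0.5 residual SD) | 3 | 63.9% | 66.8% |
| same | 5 | 63.5% | 65.2% |
| same, r 0.7 | 3 | 64.1% | 64.8% |
| same, r 0.7 | 5 | 63.9% | 63.7% |
| On change, R² 0.05 | 3 | 64.5% | 65.5% |
| On change, R² 0.10 | 3 | 65.0% | 68.1% |

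The range runs from a loss of about 2 points to a gain of about 3. Only if three covariates explained 20% of the variance of change would the gain be large (64.9% v 73.0%), and nothing in the documents supports that.

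Type I error with triggers at 0.05, 0.10 and 0.20 stayed between 4.0% and 5.2% in these runs. With a single, strongly predictive covariate (correlation 0.5 or 0.7 with the outcome) it fell to between 2.4% and 4.3%. The SF-36 analysis was not simulated.

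**The case against.** **Amyloid may already be in the CRCS model.** Objective 3 concerns the effect of MTM on CRCS over the year in PET-positive and PET-negative subjects and is tagged to both aims. The SUVR sentence sits in the same SAP paragraph as the by-group ANCOVA. It is fair to read SUVR as meant to carry into the one-year CRCS model. This stands as a possible intention, but the SAP ties SUVR to Aim 2 and lists no terms for the by-group model.

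**The MAI clause may imply that the stratum is handled.** It can be read as asking for covariates beyond stratification factors already accounted for. But it only exempts those factors from the imbalance rule and never says they are model terms. Equally, a reader might infer that the clause deliberately excludes the stratum. The text does not say that either.

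**Discretion is limited.** The baseline tests are named. The protocol lists the five candidates for its analyses generally, and Research Procedures (Blinding) says data analysis is blinded to the intervention. All this stands. It narrows the analyst's choice without supplying the threshold, and the SAP's MAI and SF-36 rules still refer to any variables.

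**Fixed covariates are not always better.** This also stands. Covariates unrelated to change cost power: from 65.0% to about 63.5% with three, 62.4% with five and 61.8% with six.

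**Conclusion.** The point holds as a minor one. Neither between-arm model states a stratum term, although randomisation is stratified on amyloid status. If amyloid status shifts one-year change, the cost is 0 to about 5 points of power, and the upper end needs an assumed 0.8 SD stratum effect. If it shifts only the level, the cost is nil for plain change and about 1 to 2 points with a baseline covariate. For MAI it may be nil, because the documents give no link between amyloid and change in MAI. Every effect size and correlation here is an assumption.

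The covariate trigger is a smaller matter: a poorer selection rule and a missing detail.

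A reader might infer that the omission or the trigger biases the result or raises the false-positive rate. Neither was shown: omitting the stratum makes the test conservative, and the triggers tested gave no inflation. A reader might also infer that fixing all five covariates would clearly raise power, but the runs show losses as well as gains.

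**What to change.** **Main change.** State in the SAP that the amyloid-PET randomisation stratum is always a term in the MAI and by-group CRCS models. Where continuous SUVR is already in the CRCS model, state that SUVR serves as the amyloid term, so that two versions of one measurement are not both needed. The cost is one degree of freedom with no visible power loss, and no new data, since PET is done on everyone at screening.

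**Secondary change.** Replace the imbalance triggers in the SAP and the two matching protocol sentences with a short list fixed before unblinding. Draw it from the five named variables and record why each is expected to relate to change in that outcome. If none is, use the amyloid term alone. Keep baseline comparisons descriptive. The cost is wording, plus 1.5 to 3 points of power if three to five fixed covariates turn out not to predict change, which is why the list should stay short.

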**Objectives:** List your research objectives. You may reference grant application/sponsor's relevant protocol pages and attach as an appendix in the E-IRB "Additional Information" section.

Specific Aim 1: Conduct a 12-month, randomized, placebo-controlled trial to evaluate the impact of our patient-centered, pharmacist-physician team MTM intervention in reducing unnecessary and inappropriate medication use in community-dwelling, elderly, non-demented subjects. Our team will specifically target the Beers 2015 list of inappropriate medications for those 65 years and older, and implement individualized, patient-centered alternative management strategies. Primary outcome measures will include pre- to post- intervention measures of: (1) use of inappropriate medications as measured by the Medication Appropriateness Index (MAI); 2) Cognitive Reserve Change Score (CRCS), defined as the difference in the scopolamine- challenged vs unchallenged measures on the neurocognitive score (defined below). Specific Aim 2: Evaluate the impact of preclinical amyloid burden on cognitive reserve deficits and decline (measured as CRCS) to evaluate efficacy of delaying symptomatic disease progression in pAD. Baseline determination of total brain relative standardized uptake values for amyloid  $\beta$ - positron emission tomography will be used to examine the relative impact of preclinical AD pathology on CRCS at baseline and over time in the placebo group, as well as the interplay of pAD pathology with inappropriate medication use at baseline and optimization of medication use after one year of MTM intervention. Objectives: 1) Examine the effectiveness of the MTM intervention in reducing inappropriate medication use over the study period as assessed by the MAI (Aim 1). 2) Investigate the effects of baseline A $\beta$ -PET and medication appropriateness index (MAI) 35 on cognitive reserve, operationalized as the CRCS = scopolamine challenged test performance z score - unchallenged cognitive test performance z score (Aim 1 and 2). 3) Investigate the effects of MTM and changes in MAI on CRCS in subjects that are A $\beta$ -PET positive or negative over the one-year study period (Aim 1 and 2).

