**Study Design:** Describe the study design (e.g., single/double blind, parallel, crossover, etc.). Indicate whether or not the subjects will receive placebo medication at some point in the research procedures. Also, indicate whether or not the subjects will be randomized in this study. You may reference sponsor's protocol pages and attach as an appendix in the E-IRB "Additional Information" section. (Including the study design table from a sponsor's protocol is helpful to IRB members.)

**Community-Based Participatory Research:** If you are conducting [community-based participatory research \(CBPR\)](#), describe strategies for involvement of community members in the design and implementation of the study, and dissemination of results from the

study.

**Research Repositories:** If the purpose of this submission is to establish a research repository describe the repository design and operating procedures. For relevant information to include, see question 22 of the UK IRB “Frequently Asked Questions (FAQs) on the Return of Research Results or Incidental Research Findings” [\[PDF\]](#).

This is a 12-month, parallel arm, placebo-controlled study to be conducted at the University of Kentucky. 90 non-demented subjects with varying levels of A $\beta$ -PET positivity (estimated that 30 will meet threshold criteria for pAD) will be randomly assigned to treatment with the MTM intervention or placebo. Those assigned in the intervention arm might have medication changes recommended by the research team. A letter describing all the proposed changes will be sent to the participant’s primary care physician (PCP). These changes will be recommended, but not forced on the participant and their PCP. The participant and their PCP will have final decision on accepting or rejecting the proposed changes in the medication plan. All subjects will undergo cognitive testing under both scopolamine challenged and unchallenged conditions within 4 weeks, as well as physical and neurologic exam, and A $\beta$ -PET scan at baseline. Cognitive testing under both scopolamine challenged and unchallenged conditions within 4 weeks, as well as physical and neurologic exam will be performed at study completion. Randomization will be stratified by A $\beta$  positivity on PET scans. If unbalanced between groups after randomization, age, gender, education, NART, and number of targeted inappropriate medications using Beers 2015 Criteria will be included in the analyses.

Attachments

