Screening Visit (Week -5 ± 2): Subject appropriateness and safety for the study will be assessed with thorough review of medical history, medication review, physical/neurological exam, vital signs, and ECG. SF-36 will assess pre- study perceived health status. Lifestyle Factor Questionnaire will further assess health history and current health status. A Baseline Questionnaire will assess motivation for participating and understanding of medications. Aβ-PET will be performed to allow stratification at baseline. Approximately 4 hours. Baseline and EOS visit (Scopolamine-challenge; week -4 ± 1 & week 52 ± 1): Subject will apply scopolamine patch at ~8pm the night before this visit to ensure adequate plasma levels of scopolamine. Study partner will drive subject to and from appointment. Medical history and medication review will be performed to ensure no changes have occurred since prior visit. Vital signs will be obtained. Cognitive testing including TMTB, MoCA, CVLT will be performed. Following cognitive testing, subject will remove scopolamine patch. Baseline and EOS visit (Non-challenge; week 0 ± 1 & week 56 ± 1): Medical history and medication review will be performed to ensure no changes have occurred since prior visit. Vital signs will be obtained. Cognitive testing including TMTB, MoCA, and CVLT will be performed. MTM intervention vs. placebo distribution of educational materials on PIM use will be performed. SF-36, Lifestyle Factors Questionnaire, and End of Study (EOS) Questionnaire will be administered at the EOS visit to assess changes in health status. Month 3 & 9 visits (week 13 ± 1 & week 39 ± 1): Telephone check to screen for adverse effects, update medical history and medication review. Month 6 visit (week 26 ± 1): Medical history and medication review will be performed to ensure no changes have occurred since prior visit. Vital signs will be obtained MTM intervention vs. placebo distribution of educational materials on PIM use will be performed. Randomization: For randomization, subjects will be stratified by Aβ positivity on PET scans; if age, gender, education, NART scores, and the number of targeted inappropriate medications using 2015 Beers Criteria are unbalanced between groups after randomization, they will be included in the analyses. Blinding: As the intervention is educational in nature, complete blinding of intervention is not possible. However, we will take the following steps in order to minimize potential bias and achieve the maximum level of blinding possible by this design: 1. When reviewing the medication list prior to the intervention, the coordinator, study pharmacist, and physician will be unaware of the group allocation. 2. Data analysis will be blinded to the intervention.

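### Covariates enter the amyloid–CRCS analysis of Aim 2 only if the randomised arms are imbalanced, which is the wrong trigger for an exposure that was not randomised

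*SAP*

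**What the plan says.** The second paragraph of the SAP (Statistical analyses) covers cognitive reserve. It opens with "Data evaluating cognitive reserve will be analyzed by intervention groups". It then says that for Aim 2 "the impact on cognitive reserve will be assessed across the full range of SUVR", with SUVR entered as a continuous variable. The next sentence is the only covariate rule in the paragraph: "If imbalance exists between groups after randomization, covariates for analysis will include age, gender, education, NART scores", and the number of targeted Beers 2015 medications. The paragraph closes with an ANCOVA of change in CRCS by group.

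The protocol repeats the condition twice. Study Design has "If unbalanced between groups after randomization, age, gender, education, NART, and number of targeted inappropriate medications using Beers 2015 Criteria will be included", and the randomisation text under Research Procedures says that if these variables "are unbalanced between groups after randomization, they will be included in the analyses".

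Protocol Objectives, Specific Aim 2, sets out to "Evaluate the impact of preclinical amyloid burden on cognitive reserve deficits and decline (measured as CRCS"). The baseline amyloid PET measure "will be used to examine the relative impact of preclinical AD pathology on CRCS at baseline and over time in the placebo group". Objective 2 likewise asks how baseline amyloid PET and MAI affect CRCS. Neither document gives a covariate set for the SUVR models that applies whatever the arm balance, or a check of covariates against SUVR.

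**The concern.** Randomisation allocates MTM or placebo. It does not allocate SUVR. Stratifying by amyloid positivity spreads amyloid evenly over the arms, but does not make SUVR independent of age, education or premorbid ability. An SUVR–CRCS association is observational, and its possible confounders are variables related to both SUVR and CRCS. A comparison of the two arms does not look at either relation. For the association within the placebo group there is no second arm in the analysis at all.

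Followed as written, the plan fits the SUVR model without age, gender, education, NART or the medication count whenever the arms happen to be balanced. Whether the Aim 2 result is adjusted then depends on the chance of allocation and on an imbalance threshold that is not stated. At stake is one of the two specific aims: an amyloid association could partly reflect age or education, or a real one could be masked.

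**Working it through.** The plan gives no power, effect size or correlation for this analysis, so there is no figure to reproduce. The check covers three things: how often the rule leaves the model unadjusted, what an uncontrolled confounder could do, and whether arm balance carries any information about it.

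**Inputs.** From the documents: N = 90; five covariates in the conditional rule; about 30 of 90 expected to be amyloid positive. Assumed: equal allocation, so about 90/2 = 45 in the placebo group; a two-sided 5% test of the association; all correlations; the imbalance threshold a.

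**1. How often the rule stays off.** With five independent tests at level a, P(none flagged) = (1 − a)^5.

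| a (assumed) | P(none flagged) |
|---|---|
| 0.01 | 95.1% |
| 0.05 | 77.4% |
| 0.10 | 59.0% |
| 0.20 | 32.8% |

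If only the flagged variable is entered, any one confounder is left out about 95% of the time at a = 0.05.

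**2. Illustrative false-positive rate.** With no true SUVR effect, a covariate correlated r1 with SUVR and r2 with CRCS induces a spurious correlation of size ρ = r1 × r2: 0.2 × 0.2 = 0.04; 0.3 × 0.4 = 0.12; 0.4 × 0.4 = 0.16. By Fisher's z, δ = atanh(ρ) × √(N − 3), and the rejection rate is Φ(δ − 1.96) + Φ(−δ − 1.96). For ρ = 0.12 and N = 90: δ = 0.1206 × √87 = 0.1206 × 9.327 = 1.125, which gives 0.202 + 0.001 = 20.3%.

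| ρ (assumed) | N = 90 | N = 45 |
|---|---|---|
| 0.04 | 6.6% | 5.8% |
| 0.12 | 20.3% | 12.2% |
| 0.16 | 32.5% | 18.2% |

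The N = 45 column is the relevant one for the association over time in the placebo group.

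**3. Does arm balance matter?** A simulation used N = 90, allocation stratified by amyloid positivity (top third), 4,000 replicates per setting, a true SUVR effect of zero, and one confounder with correlation r with SUVR and standardised effect b on CRCS. Adjustment was triggered by a 5% t-test between arms.

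| r = b (assumed) | Unadjusted bias, arms balanced | Unadjusted bias, arms imbalanced | False positives, conditional rule | False positives, always adjusted |
|---|---|---|---|---|
| 0.2 | 0.039 | 0.034 | 6.2% | 5.0% |
| 0.3 | 0.089 | 0.072 | 13.6% | 4.8% |
| 0.4 | 0.160 | 0.152 | 30.7% | 5.2% |

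Bias is in SD of CRCS per SD of SUVR. It is about r × b whether or not the arms are balanced, so the trigger does not detect it. With r = 0 or b = 0 the bias in balanced trials is about zero and the conditional rule holds its level (5.3% and 4.7%). In the placebo group alone, the conditional rule gave 8.3% at r = b = 0.3 and 17.2% at 0.4, against 4.6% and 4.3% when always adjusted.

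**The case against.** **The rule may be meant only for arm comparisons.** The sentence stands between two statements about groups, and the SAP does not say that no other covariates may enter. On this reading the Aim 2 covariates are simply unspecified. That is possible, but the rule follows directly on the SUVR sentence, it is the only one given, and the protocol applies it to the analyses without restriction. On either reading, no adjustment of the SUVR association is assured.

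**CRCS is a within-person difference.** This objection has real force. The protocol defines CRCS as the challenged minus the unchallenged z score. If a covariate X shifts the two scores by βc·X and βu·X, CRCS carries only (βc − βu)·X. An equal shift cancels, and a simple change in CRCS differences once more. So a reader might infer that the association is bound to be biased, and the documents do not support that. Bias needs a covariate that is related to SUVR and acts differently under challenge. Cancellation cannot be assumed either, since the plan itself lists age, education and NART as covariates for these analyses.

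**The numbers are assumed.** They are. A reader might take 20% or 33% as the trial's false-positive rate, or 77% as the chance that Aim 2 goes unadjusted. The documents support neither: they give no correlations and no imbalance threshold for this analysis, and the rates fall to about 12% and 18% at 45 participants. At the weakest setting the excess over 5% is trivial.

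**The primary comparisons are randomised.** Correct. A reader might extend the point to MTM versus placebo on MAI or CRCS. It does not reach them, because randomisation protects those comparisons from confounding.

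**Conclusion.** The point holds as a flaw in the covariate rule: imbalance between arms is the wrong condition for adjusting an association with an observed exposure. It applies to the SUVR–CRCS association at baseline, over time and within the placebo group. For a comparison of the MTM effect across amyloid levels, it affects only how far a difference can be attributed to amyloid.

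What is shown is that possible confounding by the five listed variables is left uncontrolled when the arms are balanced. That the result will be confounded is not shown. The size is unknown; the illustrative rates run from about 6% to 33%, depending on assumed correlations and on whether 90 or about 45 participants are analysed. The change should be made before the analysis, but it does not threaten the trial's randomised comparisons.

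**What to change.** In the SAP, separate the two rules:

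- In every model with SUVR as the exposure (CRCS at baseline, CRCS over time, and the placebo-group analysis), always enter age, gender, education, NART and the baseline count of targeted Beers medications, whatever the balance between arms.
- Confine the imbalance rule to the comparisons between arms, and align the matching sentences in the protocol (Study Design, and randomisation under Research Procedures).
- Report the SUVR result as an adjusted association.

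The plan already names all five variables. The cost is SAP and protocol wording and about 5 degrees of freedom, out of 90 participants or out of about 45 in the placebo group.

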We plan to enroll 90 participants. Eligibility and inclusion/exclusion criteria have been selected on the basis of efficacy endpoints and safety concerns and contraindications to scopolamine therapy or PET scanning to minimize the potential for adverse events. Recognized contraindications and medical conditions preventing the use of scopolamine patches or those requiring dosage adjustments will be screened for and subjects excluded from the protocol. Inclusion Criteria: 1. 65 years and older 2. Non-demented 3. No previous reaction or contraindication to scopolamine patch, or medical condition warranting dose adjustment in scopolamine including but not limited to: open angle glaucoma, gastrointestinal or urinary outlet obstructions, seizures, or psychosis. 4. No contraindications to A $\beta$ -PET scan including hypersensitivity to PET ligand or radiation exposures in the past year that would exceed the acceptable safe annual exposure in combination with the A $\beta$  PET 5. Medically stable and able to complete all study activities, as determined by the investigator 6. Reporting at least one potentially inappropriate medication as listed in the Beers 2015 criteria 7. Living in the community 8. Able to identify a study partner who will drive the participant to and from the scopolamine-challenged visits. 9. Willing to participate in this intervention study. Exclusion Criteria: 1. Allergy or other known intolerance to scopolamine patches 2. Narrow-angle glaucoma 3. Difficulty swallowing 4. Stomach or bowel problems (e.g., blockage, muscle weakness, ulcerative colitis) 5. Bleeding 6. Myasthenia gravis 7. Blockage of the urinary tract. 8. Seizures 9. Psychosis

Attachments

**Subject Recruitment Methods & Privacy:** Describe plans for the identification and recruitment of subjects, including how the population will be identified, and how initial contact will be made with potential subjects by those having legitimate access to the subjects’ identity and the subjects’ information. Describe the setting in which an individual will be interacting with an investigator. If applicable, describe proposed outreach programs for recruiting women and minorities as participants in clinical research.

Please note: Based upon both legal and ethical concerns, the UK Medical Institutional Review Board (IRB) will not approve finder’s fees for research studies.

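### The SF-36 MANCOVA yields one non-directional joint test with no rule for domain-level conclusions, and neither the screening SF-36 score nor the amyloid stratum is a planned covariate

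*SAP*

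**What the plan says.** The last paragraph of the SAP's Statistical analyses section is the whole analysis plan for the SF-36. It chooses the method "because the SF-36 does not produce a single overall measure and because of our concern regarding multiple comparisons", and states that "multivariate analysis of covariance (MANCOVA) will be used to simultaneously estimate the effect of the intervention on the eight SF-36 health concepts". On covariates it says: "Similarly, we will also control for any variables that might be significantly different between groups at baseline". It gives no alpha, decision rule, domain-level test, adjustment after the joint test or summary score. It does not say whether the dependent variables are end-of-study scores or changes.

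In the protocol, Research Procedures places the SF-36 at the screening visit, before randomisation, and again at the end of study (EOS), where it "will be administered at the EOS visit to assess changes in health status". Study Design and Research Procedures both stratify randomisation by amyloid PET positivity. Objectives lists the MAI and the CRCS as primary outcome measures; the SF-36 is not among them.

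**The concern.** The purpose given in the protocol, to see how health status changed, has a direction. The reason given in the SAP, "because of our concern regarding multiple comparisons", is about error across eight domains. A MANCOVA arm test meets neither in full. It tests whether the two arms differ in any way across eight means, so benefit, harm and a mixture all count as rejection. Its error guarantee applies when no domain differs. Once one domain truly differs, the joint test tends to reject and gives little protection to statements about the other seven.

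At stake is how the SF-36 result is reported. If the joint test is significant, readers will want to know which domains moved and which way, and the SAP has no rule for saying so. That rule would then be set after the data are seen, or domain results would be reported without adjustment. Separately, the covariate rule leaves out the two variables with the best claim to be in the model: the pre-treatment value of the same measure and the stratification factor.

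**Working it through.** The documents contain no power or sample-size figure for the SF-36, so there is nothing to reproduce. The check asks what the joint test can and cannot show.

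**Inputs from the documents.** Eight dependent variables ("the eight SF-36 health concepts"). N = 90 ("We plan to enroll 90 participants", protocol, Study Population). Two arms: participants "will be randomly assigned to treatment with the MTM intervention or placebo" (protocol, Study Design).

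**Assumptions, because the documents give none.** Allocation 1:1, so n = 45 per arm. Alpha 0.05. Standardised domain effects δ as listed below. A common inter-domain correlation ρ, 0.5 unless another value is shown. No dropout unless stated.

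**Formulae.** With two arms every MANCOVA criterion reduces to Hotelling's T². Without covariates the test is F with 8 and 90 − 2 − 7 = 81 df. Its noncentrality is

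λ = (n/2) δ′R⁻¹δ = (n/2) × [Σδ² − ρ(Σδ)²/(1 + 7ρ)] / (1 − ρ).

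The comparator composite is the mean of the eight standardised scores (1 df), with effect mean(δ) × √(8/(1 + 7ρ)). For Holm, the figure is the chance that at least one domain passes the first step, 0.05/8 = 0.00625, by simulation.

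**1. Direction.** λ is quadratic in δ, so reversing every sign leaves it unchanged. At ρ = 0.5:
- All eight better by 0.3: λ = 22.5 × [0.72 − 0.5 × 5.76/4.5]/0.5 = 22.5 × 0.16 = 3.6; power 19.7%. All eight worse by 0.3 gives the same 19.7%.
- Four better and four worse by 0.3: λ = 22.5 × 0.72/0.5 = 32.4; power 98.8%.

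**2. Domain statements.** These figures come from simulating a significant joint test followed by each domain at an unadjusted 0.05. The SAP does not state that follow-up; it shows what happens if nothing else is specified.
- No domain differs (ρ = 0.5): at least one false domain claim in 3.9% of trials.
- One domain truly differs by 0.8 SD: at least one false claim among the other seven in 26% (ρ = 0), 23% (ρ = 0.5) and 18% (ρ = 0.7) of trials. The ceiling for seven independent tests is 1 − 0.95⁷ = 30%.
- Holm across the eight domains, one domain differing by 0.8 SD at ρ = 0.5: 4.0%.

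**3. Power by pattern of effect**, ρ = 0.5 unless shown:

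| Pattern of true gains (SD) | λ | MANCOVA | Holm, at least one | 1-df composite |
|---|---|---|---|---|
| 0.4 in all eight | 6.4 | 35% | 56% | 71% |
| 0.2 to 0.6, evenly spaced | 12.6 | 66% | 72% | 71% |
| 0.2 to 0.6, ρ = 0.7 | 15.2 | 76% | 63–64% | 59% |
| 0 to 0.6, evenly spaced | 17.5 | 83% | 66–67% | 47% |
| 0.4 in four, 0 in four | 16.0 | 79% | 44–45% | 24% |
| 0.5 in one, 0 in seven | 10.0 | 54% | 36% | 7% |

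Example, row 1: 22.5 × [1.28 − 0.5 × 10.24/4.5]/0.5 = 22.5 × 0.2844 = 6.4. Row 5: 22.5 × [0.64 − 0.5 × 2.56/4.5]/0.5 = 22.5 × 0.7111 = 16.0. Any spread between domains adds to λ, so the exactly uniform gain is an unfavourable case for MANCOVA.

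For the uniform 0.4 gain over ρ = 0.7 to 0.3, MANCOVA has 26–50% power and the composite 59–85%. At 38 per arm (about 15% dropout) the ranges are 22–42% and 52–79%. For a uniform 0.5 gain at 45 per arm, MANCOVA has 41–74%. Spending df on eight covariates changes MANCOVA power by less than 1 point.

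**4. Covariates.** Under randomisation, a given domain's screening score differs significantly between arms about 5% of the time at a 0.05 level, so the stated rule would usually leave it out. Stratification keeps the amyloid groups balanced by design, so a significance rule will hardly ever select the stratum. The SAP's MAI paragraph also sets aside variables already used for stratification.

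**The case against.** MANCOVA is a recognised method for correlated outcomes with no overall score, and that is one of the SAP's two reasons for it. For the single joint test actually planned, type I error is controlled. Both points stand.

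A reader might infer from the uniform-gain row that MANCOVA is underpowered and should be replaced. The documents do not support this. They give no SF-36 effect size or correlation and do not say that benefit would be equal across domains. With modest variation in the gains the three approaches come close together, and with partial effects MANCOVA is clearly ahead. Choosing among global tests is a trade-off, not a correction.

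A reader might also infer that the SAP plans unadjusted domain tests and so accepts 18–26% false claims. It does not; it plans no domain tests at all. The fault is a missing rule, not a wrong one.

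Nor is it right that the analysis can say nothing about direction. The fitted model gives eight signed adjusted differences. What is missing is a stated way to turn them into conclusions. The mixed pattern of four domains up and four down is artificial and only shows that the test has no sign.

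On covariates, a generous reader could take the screening SF-36 scores as implied by the word covariance. The text does not name them, and the only rule it gives selects on baseline significance.

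**Conclusion.** The point holds in a limited form. The joint test is non-directional and protects only the case where no domain differs, so on its own it does not support a claim that perceived health or a given domain improved. That follows from the form of the test. The percentages attached to it depend on the assumed allocation, alpha, correlation and effect sizes. The gap in domain-level rules and the absence of the screening score and amyloid stratum as planned covariates can be read directly from the SAP.

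Low power is not part of the conclusion: in the patterns tried at ρ = 0.5, MANCOVA ranged from 21 points below Holm (35% against 56%) to about 34 points above it (79% against 44–45%). Because the SF-36 is not a listed primary outcome, the priority is minor.

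**What to change.** Keep MANCOVA as the global test if wanted, and state its alpha. Add that domain-level conclusions will come from eight ANCOVAs of the end-of-study score, each adjusted for that domain's screening score and the amyloid stratum. Report all eight signed differences with 95% CIs and Holm-adjusted p-values. For the SF-36, specify these covariates in advance instead of selecting them on baseline significance. A 1-df composite is optional. If it is added, note that it is weak when effects oppose each other and also when gains are confined to a few domains.

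The cost is SAP wording and a little more analysis. The screening and end-of-study SF-36 and the stratum are already collected, so no visit or instrument changes. The downside is that Holm is somewhat conservative for correlated domains.
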